### **Trial Objective and Purpose:**

The purpose of this trial is to determine if the upstream use of metformin in patients with atrial fibrillation and obesity undergoing a rhythm control strategy will increase the frequency of maintenance of sinus rhythm at six months. The primary endpoint is the number of patients in normal sinus rhythm after six months of follow up. Secondary endpoints are amount of weight loss, change in BMI, change in hemoglobin A1c, number of thromboembolic events, and burden of atrial fibrillation based on the Atrial Fibrillation Severity Score (AFSS).

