#### **Trial Design:**

The proposed study will be a randomized control trial comparing metformin therapy to a control group in patients with a BMI  $\geq$ 27 and atrial fibrillation who have elected to undergo a rhythm control strategy with ablation. Upstream therapy with Metformin will be used in a randomized fashion. The only variation to the standard of care will be the addition of Metformin therapy and additional blood draws for safety monitoring and EKGs for measuring outcomes in both the intervention and control groups.

Patients meeting the below inclusion and exclusion criteria who provide informed consent will be randomized to control versus metformin therapy six weeks prior to rhythm control.

At baseline all study patients will be assessed for:

Age, Gender, Weight, BMI, Tobacco Use, Hypertension, Hemoglobin A1c, Hyperlipidemia, serum CRP, glomerular filtration rate estimating equation (eGFR), B12, liver function tests (AST, ALT, ALP, bilirubin, albumin, INR), lactic acid, History of Coronary Artery Disease by MI, PCI, or CABG, History of Valvular Disease, History of Obstructive Sleep Apnea, Type of AF and duration, Number of Antiarrhythmic Medications (not including beta-blockers or calcium channel blockers).

In addition, patients will fill out a survey to determine their Atrial Fibrillation Severity Score (AFSS) - a validated tool to assess the symptomatic burden of AF - and will receive education on dietary changes and exercise

Metformin will be initiated at 500 mg daily and increased as tolerated to 2000 mg daily over a three week period. Subjects will be instructed to hold Metformin on the day of any procedure or study requiring the administration of intravenous contrast and to resume 48 hours after the contrast administration and reinstituted only after renal function has been reevaluated and found to be at the patient's baseline. All patients will receive information on dietary changes to promote weight loss and will be encouraged to increase exercise activities. Patients will discontinue treatment at any time they are found to meet the baseline exclusion criteria for the study.

The initiation of the drug and the dosage increases will be overseen by a designee (mid-level cardiology practitioner) who will be responsible for stopping dosage increases if side effects occur. Six weeks after the initiation of drug the patient will undergo ablation with the intent of achieving rhythm control.

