Patients will be followed up in regular intervals after the initial attempt at rhythm control. The minimum follow up interval is every three months. More frequent follow up may be scheduled as deemed necessary by the treating physician.

[figure not shown]
At the time of the first attempt at rhythm control, at the 3 month follow up, and at the 6 month follow up all study patients will be assessed again for:

Weight, BMI, Hemoglobin A1c, serum CRP, eGFR, liver function tests (AST, ALT, ALP, bilirubin, albumin, INR), B12, lactic acid, number of antiarrhythmic agents, presence of AF by EKG, and Atrial Fibrillation Severity Score.

At each 3-month and 6-month follow up, data will be reviewed by a designee who will use the criteria described below for reporting to the Medical Monitor. The patient will also be assessed for the occurrence of any adverse events as defined below and adverse events will be reported to the medical monitor.

At the end of 6 months of therapy, the decision to continue Metformin beyond 6 months will be made in conjunction with the patient's treating cardiologist and primary care physician.

Figure 1.

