#### **Outcomes and Assessment of Efficacy:**

The primary outcome by intention to treat analysis will be maintenance of sinus rhythm by chart review, EKG, and Atrial Fibrillation Severity Score at 3 and 6 months after the initial attempt at rhythm control.

Secondary outcomes will include hospitalization related to arrhythmic events or medication side effects, number of antiarrhythmic medications, number of repeat ablations, BMI, Hemoglobin A1c, and number of thromboembolic events.

Pre-specified subgroup comparisons will include comparing patients randomized to metformin who have a 5% reduction in weight at 6 months to all control patients who achieve a 5% reduction in weight, and to all control patients.

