#### **Statistics:**

We expect a 30% recurrence of AF after patients undergo ablation. After ablation, we expect the recurrence of AF to be 30% less in the intervention group of patients on metformin than the control group.

Using an 80% power at a 95% confidence interval, the sample size of the control group (ablation only) and the intervention group (ablation plus metformin) will be 400 each for a two tailed study, accounting for up to a 3% attrition rate in each group. The total sample size of this study will be 800. It is estimated to take five years to accrue subjects.

Statistical methods employed to analyze outcomes will be a Pearson's  $X^2$  test for categorical variables. Analysis of Variance will be used for continuous variables. All tests are two-sided and P < .05 will be used to indicate a statistically significant difference.

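### The metformin continuation decision is timed from drug start, so the wording permits stopping about six weeks before the 6-month primary reading

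*Combined protocol and SAP*

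**What the plan says.** The combined protocol and SAP uses two starting points for time.

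- **Drug start.** Trial Design: "Six weeks after the initiation of drug the patient will undergo ablation with the intent of achieving rhythm control". The continuation decision, in the same section, is also expressed in time on treatment: "At the end of 6 months of therapy, the decision to continue Metformin beyond 6 months will be made". It is shared between the treating cardiologist and the primary care physician.
- **Ablation.** Trial Design, on visits: "Patients will be followed up in regular intervals after the initial attempt at rhythm control". Outcomes and Assessment of Efficacy reads the primary outcome, by intention to treat, "at 3 and 6 months after the initial attempt at rhythm control". Trial Objective and Purpose: "The primary endpoint is the number of patients in normal sinus rhythm after six months of follow up".

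On visit frequency, Trial Design says "The minimum follow up interval is every three months" and adds "More frequent follow up may be scheduled as deemed necessary by the treating physician".

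The Statistics section ties the assumed effect to drug exposure: "we expect the recurrence of AF to be 30% less in the intervention group of patients on metformin than the control group".

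No readable sentence requires metformin to continue until the 6-month post-ablation reading. None says that six months of therapy means the 6-month follow-up visit.

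**The concern.** Time on therapy most naturally runs from the first dose. On that reading the decision point comes before the primary reading, because the six weeks of pre-treatment count towards the six months. A patient could then stop the randomised drug shortly before the outcome is measured, without a protocol deviation.

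Under intention to treat, such a patient stays in the metformin arm. If the benefit fades after stopping, the 6-month rhythm contrast moves towards no effect. The 6-month weight, BMI and HbA1c comparisons could move the same way. Only the metformin arm is affected, and the loss would be avoidable.

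**Working it through.** **1. The plan's own sample size.** Inputs from Statistics: 30% recurrence in controls; 30% less on metformin, read as relative, so 0.30 × 0.70 = 21%; two-sided 0.05; 80% power; up to 3% attrition; 400 per arm.

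The pooled-variance formula, with p̄ = (p₁ + p₂)/2, is

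n = [1.96·√(2p̄(1−p̄)) + 0.842·√(p₁(1−p₁) + p₂(1−p₂))]² / (p₁ − p₂)²

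- Without continuity correction: 367 per arm; 367/0.97 gives 379 after attrition.
- With continuity correction, n_c = (n/4)·[1 + √(1 + 4/(n·|p₁ − p₂|))]²: 389 per arm; 389/0.97 gives 402.

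The corrected version best matches the stated 400. Evaluable patients per arm: 400 × 0.97 = 388.

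**2. Timeline on the literal reading, taking 6 months as 26 weeks.**

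| Event | Weeks from drug start | Weeks from ablation |
|---|---|---|
| Drug start | 0 | −6 |
| Ablation | 6 | 0 |
| 3-month reading | about 19 | 13 |
| Continuation decision | about 26 | about 20 |
| 6-month primary reading | about 32 | 26 |

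The gap is 32 − 26 = 6 weeks, or 6/26 = 23% of the post-ablation window. The 3-month reading comes before the decision and is unaffected.

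**3. Illustration of possible dilution.** The stop rate, the constant hazard and the loss of effect on stopping are assumptions; none is in the documents. The model also treats the 6-month outcome as recurrence accumulated over 26 weeks.

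- Weekly hazards: control −ln(0.70)/26 = 0.01372; metformin −ln(0.79)/26 = 0.00907.
- Full loss: a stopper has the metformin hazard for 20 weeks and the control hazard for 6. Recurrence = 1 − exp[−(20 × 0.00907 + 6 × 0.01372)] = 23.2%.
- Half loss: the last 6 weeks use the mean of the two hazards. Recurrence = 22.1%.
- Metformin-arm rate with a share s stopping: p₂ = 21% + s × (stopper rate − 21%).
- Power = Φ{[Δ − 1.96·√(2p̄(1−p̄)/388)] / √([p₁(1−p₁) + p₂(1−p₂)]/388)}, where Δ = p₁ − p₂. The continuity-corrected version uses Δ − 1/388.

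No stopping: Δ = 0.09, and (0.09 − 1.96 × 0.03129)/0.03113 = 0.921, so power is 82.1%. With correction it is 79.9%.

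25% stopping, full loss: p₂ = 21.54% and Δ = 0.0846, and (0.0846 − 1.96 × 0.03140)/0.03125 = 0.736, so power is 76.9%. With correction it is 74.3%.

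| Share stopping | Full loss: arm rate | Power | Power, corrected | Half loss: arm rate | Power |
|---|---|---|---|---|---|
| 0% | 21.0% | 82.1% | 79.9% | 21.0% | 82.1% |
| 10% | 21.2% | 80.2% | 77.8% | 21.1% | 81.2% |
| 25% | 21.5% | 76.9% | 74.3% | 21.3% | 79.6% |
| 50% | 22.1% | 71.0% | 68.1% | 21.5% | 76.9% |
| 100% | 23.2% | 57.6% | 54.4% | 22.1% | 70.9% |

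If the effect outlasts the drug by six weeks, power does not change at any stop rate.

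**The case against.** The strongest reply is that the sponsor simply meant the 6-month visit. The sentence follows directly on text about the 3- and 6-month follow-ups, and the other six-month milestones in the document refer to that visit. No contact is scheduled near week 20 after ablation, and drug return and accountability take place at visits. Figure 1, which sits beside this text, is not shown in the copy reviewed and may settle the matter. All of this stands, and it makes the benign reading quite plausible. It does not remove the ambiguity: the sentence counts therapy, the neighbouring text counts follow-up, extra visits are allowed, and a decision shared with the primary care physician need not wait for a study visit.

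The second reply is that the size of any harm is assumed. That also stands. The last row of the table has every patient stopping and reverting at once to the control hazard, which fits poorly with an upstream mechanism working through weight loss and AMPK activation.

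A reader might infer two stronger things. One is that the protocol ends treatment at six months; it does not, because the sentence sets a decision point, not a stop order. The other is a stop rate above which power drops below the planned 80%. No such threshold should be quoted. It depends on the formula: power with no stopping is 82.1% uncorrected, but 79.9% with the correction that best matches 400 per arm, which leaves no margin to use up.

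**Conclusion.** The point holds as a minor defect of wording. Read literally, the plan allows randomised metformin to stop about 6 weeks before the primary reading, and no readable text requires the drug up to that reading. Whether anyone would stop, and what it would cost, cannot be estimated from the documents; the dilution may be zero. The drop from 82% to 77% (80% to 74% with correction) at 25% stopping assumes a constant hazard and immediate, complete loss of effect. It shows scale and is not a forecast.

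It would be wrong to infer that the primary result is biased in metformin's favour or that the trial is shown to be underpowered. Randomisation and the intention-to-treat comparison remain valid, any dilution is towards no effect, there is no added false-positive risk, and the sample size needs no change.

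**What to change.** Replace the continuation sentence in Trial Design with:

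> Metformin will continue, as tolerated and subject to the existing safety stopping criteria, through the 6-month post-ablation assessment. Whether to continue it after that visit will be decided, once the visit's assessments are recorded, jointly with the treating cardiologist and the primary care physician.

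If Figure 1 already shows treatment through that visit, this only brings the text into line with it.

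Cost: up to about 6 more weeks of study drug (about 32 instead of 26) for patients who would otherwise stop at six months of therapy, under the laboratory monitoring already planned at 3 and 6 months. The change also needs IRB approval as an amendment (Ethics section), with the consent wording aligned if it gives a 6-month treatment duration. No extra patients, visits or data fields are needed; drug accountability is already planned at each visit (Study Drug Compliance).

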### **Investigational Product:**

Severity Score.

An investigational product is defined a pharmaceutical form of an active substance or placebo being tested or used as a reference in a clinical study, including products already with a marketing authorization but used or assembled (formulated or packaged) differently than the authorized form, or used for an unauthorized indication, or when used to gain further information about the authorized form.

In this protocol, the investigational product is: GLUCOPHAGE® (metformin hydrochloride) tablets. The investigational product is available commercially. The outpatient pharmacy will obtain the investigational product.

The investigational product will be stored in a secure area according to local regulations. The investigator will ensure that investigational product is only dispensed to study subjects.

#### **Storage and Dispensing:**

The study drug is commercially available. Study drug will be stored in accordance with the package insert at  $20^{\circ}-25^{\circ}$  C ( $68^{\circ}-77^{\circ}$  F); excursions permitted to  $15^{\circ}-30^{\circ}$  C ( $59^{\circ}-86^{\circ}$  F).

Investigational product documentation will be maintained that includes all processes required to ensure drug is accurately administered. This includes documentation of drug storage, administration and storage temperatures.

Per package insert: The usual starting dose of GLUCOPHAGE® Tablets is 500 mg twice a day or 850 mg once a day, given with meals. Dosage increases should be made in increments of 500 mg weekly or 850 mg every 2 weeks, up to a total of 2000 mg per day, given in divided doses.

In this study the starting dose will be 500 mg daily, given with meals. Over a 3 week period, the dosage will be increased to 2000 mg daily (given in a divided dose of 1000 mg twice a day) as tolerated by the patient, according to the schedule below.

Figure 2.

Study Drug	Week 1	Week 2	Week 3	Week 4
Number of pills in Morning	1	1	2	2
Number of pills in Evening	0	1	1	2
Total pills per day	1	2	3	4
Daily dose (of 500 mg tablet)	500 mg	1000 mg	1500 mg	2000mg

# **Method of Assigning Subject Identification:**

The study design is a randomized control trial. After the subject's initial eligibility is established and informed consent has been obtained, the subject will be enrolled into the study by obtaining a randomly assigned subject number. The subject number will determine the randomization to the treatment or control arm

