### **Treatment of Subjects:**

At baseline all study patients will be assessed for:

Age, Gender, Weight, BMI, Tobacco Use, Hypertension, Hemoglobin A1c, Hyperlipidemia, serum CRP, eGFR, liver function tests (AST, ALT, ALP, bilirubin, albumin, INR), History of Coronary Artery Disease by MI, PCI, or CABG, History of Valvular Disease, History of Sleep Apnea, Type of AF and duration, Number of Antiarrhythmic Medications (not including beta-blockers or calcium channel blockers).

In addition, patients will fill out a survey to determine their Atrial Fibrillation Severity Score (AFSS) – a validated tool to assess the symptomatic burden of AF - and will receive education on dietary changes and exercise.

Subjects will be randomized to receive either Metformin (500 mg tablet) or into the control group. Subjects will be instructed to take one tablet twice a day with meals. Over a 3 week period, the dosage will be increased to 2000 mg daily (given in a divided dose of 1000 mg twice a day) as tolerated by the patient.

Patients will be followed up in regular intervals after the initial attempt at rhythm control. The minimum follow up interval is every three months. More frequent follow up may be scheduled as deemed necessary by the treating physician.

At the time of the first attempt at rhythm control, at the 3 month follow up, and at the 6 month follow up all study patients will be assessed again for:

Weight, BMI, Hemoglobin A1c, serum CRP, eGFR, liver function tests (AST, ALT, ALP, bilirubin, albumin, INR), number of antiarrhythmic agents, presence of AF by EKG, Atrial Fibrillation Severity Score, occurrence of adverse events.

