#### **Assessment of Safety:**

A Medical Monitor will be utilized to provide general oversight and safety considerations for this study. The Medical Monitor will provide advice to the Sponsor-Investigator regarding actions the committee deems necessary for the continuing protection of subjects enrolled in this study. The Medical Monitor will be charged with assessing such actions in light of an acceptable risk/benefit profile for metformin. The Medical Monitor will act in an advisory capacity to the Sponsor-Investigator and will monitor subject safety data for the study.

All patients included in the study will have monitoring of renal function, hepatic function, and serum lactic acid at baseline, at the time of ablation or initiation of rhythm control, and at 3-month and 6-month follow ups. This data will be reviewed by an investigator who is not involved in the outcome analysis. This investigator will be a mid-level who will be assigned to check the routine labs. The parameters for immediate reporting to one of the study coordinators are the following- creatinine greater than or equal to 1.5 in males or 1.4 in females, elevated lactic acid, or serum bilirubin >1.5x the upper limit of normal. Exclusion criteria will also be reviewed at each follow up, and if at any point a patient meets the exclusion criteria for the study or has an unexpected adverse event they will be withdrawn from the study.

Routine reports will be provided to the Medical Monitor every 2 months and will include rates of disenrollment, reason for disenrollment, unexpected adverse events, and mortalities. If a statistically significant harm is detected in the analysis of the safety data collected at 2 month intervals the protocol will be terminated.

Adverse events will be solicited at routine follow-up with a designee and are defined as follows: .

Lactic Acidosis – lactic acid >2.1 mmol/L as measured at either routine follow up or if measured during a hospitalization for any reason

Thromboembolic event – any stroke, mesenteric ischemia, limb ischemia, or other event determined to be of an embolic etiology secondary to atrial fibrillation Vitamin B12 levels and any change from baseline at the 3 and 6 month timepoints will be measured and submitted.

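### The primary rhythm outcome is classified from chart, EKG and a patient-completed score in a trial without placebo, and no masking of the classifiers is stated

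*Combined protocol and SAP*

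**What the plan says.** **Comparison.** Treatment of Subjects states: "Subjects will be randomized to receive either Metformin (500 mg tablet) or into the control group". Trial Design adds: "The only variation to the standard of care will be the addition of Metformin therapy", apart from blood draws and EKGs done in both arms. The Statistics section describes the arms as ablation only and ablation plus metformin. No placebo is described.

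**Primary outcome.** Outcomes and Assessment of Efficacy gives it, by intention to treat, as "maintenance of sinus rhythm by chart review, EKG, and Atrial Fibrillation Severity Score at 3 and 6 months". No assessor is named, no masking is stated, and there is no rule for combining the three sources. Trial Objective and Purpose words the primary endpoint differently, as the count of patients in normal sinus rhythm at six months, and lists the Atrial Fibrillation Severity Score (AFSS) as a secondary measure of burden. Patients complete the AFSS themselves.

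**Separation of roles.** Assessment of Safety contains the only one, and it concerns the safety laboratory results: "This data will be reviewed by an investigator who is not involved in the outcome analysis".

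**Allocation.** After eligibility and consent, "the subject will be enrolled into the study by obtaining a randomly assigned subject number", and "The subject number will determine the randomization to the treatment or control arm". Who holds the list is not stated.

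**The concern.** Two of the three sources for the primary outcome are open to influence by knowledge of the arm. Chart review requires someone to judge what an entry means, and in this trial the chart will ordinarily show whether metformin was dispensed. The AFSS is filled in by patients who know what they are taking. EKG reading is the least subjective of the three, but an equivocal tracing still needs a decision. Without a rule for combining the sources, the person who reconciles them has further discretion.

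If borderline records are resolved even slightly differently by arm, the difference enters the primary comparison as though it were a treatment effect. The chi-square test cannot tell the two apart, so the nominal 5% error rate would no longer hold.

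**Working it through.** **1. Inputs from the Statistics section.** Control recurrence 30%; 30% relative reduction, so 0.30 × 0.70 = 21% on metformin, a difference of 9 points; two-sided 5% level; 80% power; 400 per arm including up to 3% attrition; Pearson chi-square test. Evaluable per arm: 400 × 0.97 = 388.

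**2. The plan's own figure.** With p̄ = 0.255:

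n = [1.960 × √(2 × 0.255 × 0.745) + 0.842 × √(0.30 × 0.70 + 0.21 × 0.79)]² / 0.09² = 367 per arm.

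The continuity correction, (n/4) × [1 + √(1 + 4/(n × 0.09))]², gives 389, and 389/0.97 rounds up to 402. The stated 400 is reproduced to within rounding. Masking does not change this number.

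**3. Effect of a classification shift when metformin does nothing.** Assume true recurrence of 30% in both arms and a net arm-dependent shift d in the classified proportions (0.30 ± d/2).

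SE = √(2 × 0.30 × 0.70 / 388) = 0.0329.

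P(reject) ≈ [1 − Φ(1.960 − d/SE)] + Φ(−1.960 − d/SE).

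| Assumed net shift d | Equivalent patients (d × 388) | d/SE | Two-sided error |
|---|---|---|---|
| 0 | 0 | 0 | 5.0% |
| 2 points | about 8 | 0.61 | 9.3% |
| 3 points | about 12 | 0.91 | 14.9% |
| 5 points | about 19 | 1.52 | 33.0% |

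The patients may all fall in one arm or be split between the two in opposite directions. At 3 points, the favoured direction contributes 1 − Φ(1.048) = 14.7% and the other Φ(−2.872) = 0.2%, so almost all the excess goes one way.

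**4. The same question from the other side.** Suppose a share m of metformin recurrences is classified as sinus rhythm. At m = 10%, about 12 of the expected 116 recurrences, the metformin rate becomes 27% and the total error is about 15%. At m = 5% it is 7.5%, and at m = 20% it is 47%.

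**5. Smallest significant difference.** With 116 of 388 control recurrences, the test first reaches significance at 91 in the other arm, a difference of 25 patients (z = 2.03).

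None of the shifts in steps 3 and 4 comes from the documents. They show sensitivity, not an expected bias.

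**The case against.** **The subject number.** A reader might infer that the allocation wording is itself the fault, because the identifier carries the arm. The documents do not support that. The number is random, is issued after eligibility and consent, and is nowhere said to display the arm. Any identifier can be linked to the arm by whoever holds the list. What remains is that the protocol does not keep the list from those who classify rhythm.

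**The safety-laboratory separation.** A reader might also infer that the subject number defeats this safeguard. It does not: the provision concerns who reviews safety results and was never described as masking outcome assessors.

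**Inference from silence.** The protocol never calls itself open-label or its readers unmasked. This stands as a caveat. However, the outcome, statistics and allocation sections, where masking would be expected, are present and do not mention it.

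**Little judgement in an EKG.** If the endpoint is rhythm at the six-month visit, as Trial Objective and Purpose has it, there is less to misjudge, and a brief episode between visits might not count. This has force, but Outcomes and Assessment of Efficacy adds chart review and the AFSS, and that is where the exposure lies.

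**Irreparable bias.** It would be too strong to say that bias is certain or that nothing could be done later. Record Retention keeps source documents, so tracings could be de-identified and re-read masked. That would not help the patient-completed score.

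**Conclusion.** The concern holds as a risk in how the primary outcome is classified. It rests on three things in the text: no placebo, a primary outcome drawn partly from chart review and a patient-reported score, and no stated masking of the classifier. That the abstractor will see metformin in the chart is an inference about ordinary practice.

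The size of any bias cannot be derived from the documents. On the assumptions shown, a shift of 2 to 5 points, equivalent to roughly 8 to 19 patients, takes the two-sided error from 5% to between 9% and 33%. With no shift it stays at 5%. The planned effect is only 9 points, so a shift of a few points would matter. The sample size is unaffected. The sponsor should act on this before outcome data are classified, because a prespecified masked classification is more convincing than a later re-reading.

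**What to change.** **Outcomes and Assessment of Efficacy.** State that rhythm at 3 and 6 months is classified by existing outcome investigators who take no part in that patient's titration, drug accountability or follow-up. They work from EKG tracings and chart extracts with drug and arm references removed. The classification is locked before it is joined to the allocation.

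Base that classification on the EKG and documented rhythm, in line with the six-month sinus-rhythm endpoint in Trial Objective and Purpose. Report the AFSS separately, as the secondary endpoint that section already lists, because masking staff cannot protect a score completed by patients who know their arm.

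**Method of Assigning Subject Identification.** Add one sentence that the allocation list is not available to the classifiers. The random subject number can stay.

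**Cost.** No extra visits, patients or procedures are needed. Existing staff other than the classifier must prepare the redacted extracts, which is real but modest work in an 800-patient trial. Some bias may remain: what patients report can still reach the chart, and extra visits are discretionary ("More frequent follow up may be scheduled as deemed necessary by the treating physician"), so detection could still differ by arm.
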